2. OBJECTIVES, OUTCOMES MEASURES AND HYPOTHESES

OBJECTIVES	OUTCOME MEASURES	HYPOTHESES

Primary objective
 
To investigate the effect of labelling (kcal or PACE) on the total self-served energy among participants of lower and higher SEP.
	
Total self-served energy in kcal from hypothetical meals
	
Labelling (kcal or PACE) will influence the size of self-served portion and result in reduced total self-served energy among both participants of lower and higher SEP.
 
Kcal and PACE labelling will exert a stronger effect on self-served energy among participants of higher compared to lower SEP.

		PACE labelling will exert a stronger effect on self-served energy than kcal labelling.
Secondary objectives To investigate the psychological processes that may explain the different effect of the intervention and whether health motivation and physical activity level mediate the differential effect of labelling (kcal or PACE) on total self-served energy among participants of lower and higher SEP.	Executive function (tasks) Health motivation in food choices (questionnaire)	Participants of higher SEP will have better executive function than participants of lower SEP, which will moderate the relationship between SEP and the effect of energy/PACE labelling on the total energy of the selected meal. Kcal/PACE labelling will exert a stronger effect on self-served energy among participants of higher SEP because they will be more motivated by health in their food choices than participants of lower SEP.

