7. STATISTICAL ANALYSES

All statistical analyses will be performed using SAS version 9.3 (SAS Institute, Inc., 2012 SAS® 9.3. Cary, NC). The level of significance will be set at $p < 0.05$ for the main and sensitivity analyses, $p < 0.01$ for secondary analyses and $p < 0.001$ for exploratory analyses unless otherwise specified. Linear mixed models will be fitted with PROC MIXED.

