7.5. Main analyses

The primary aim of the statistical analyses will be to test the effect the labelling intervention and SEP on self-served energy. Secondary analyses will be run in order to investigate the role of potential mediators to explain the relationship SEP-self-served energy. The measure of SEP used in our main analyses will be the *highest educational qualification* (binary variable: *lower vs. higher*) because previous research showed that people of higher education were more likely to use nutrition labels [35], [36].

² MET-minutes: Metabolic Equivalent of Task of an activity × minutes performed.

Linear mixed effect models will be run in order to test the effect of the labels and of highest educational qualification on the self-served energy, with participants and dishes set as random effects to account for correlation between repeated measures by the same participant and across the different food items. The main model will test the effect of the labelling intervention (four levels: kcal labelling, PACE labelling, kcal and PACE labelling, no labelling), highest educational qualification (two levels: lower, higher) and the interaction between labelling intervention and highest educational qualification. If the interaction is significant, analyses will be stratified by *highest educational qualification (lower and higher)* and two linear mixed models will be fitted to examine the effect of the labelling intervention on self-served energy.

If there is a main effect of the labelling intervention in one of the above linear mixed models we will follow up this main effect by conducting the following pairwise comparisons:

- Self-served energy in each of the three labelling conditions compared to no labelling condition:
 - o No labelling vs. kcal labelling
 - o No labelling vs. PACE labelling
 - o No labelling vs. kcal and PACE labelling combined
- Self-served energy in the combined labelling condition compared to single labelling conditions
 - o Kcal and PACE labelling combined vs. kcal labelling
 - o Kcal and PACE labelling combined vs. PACE labelling
- Self-served energy in one single labelling condition compared to the other single labelling condition:
 - o Kcal labelling vs. PACE labelling

We will apply a Bonferroni correction to the level of significance based on the number of pairwise comparisons made (e.g., 12 comparisons: $0.05/12=0.004$).

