7.9. Sample size

A meta-analysis of six studies investigating the impact of kcal labelling on energy consumed from a single food did not demonstrate a statistically significant effect [11]. However the designs of these studies were different from the present study: the food options were mainly snacks (only one study offered to consume main meals [38]) and participants were not aware of the amount of kcal they actually consumed (the label was placed on the container or packaging, adjacent to the food, or presented on a display board). In our design, we expect a significant effect of kcal labelling with a reduction of 8.4% of self-served energy per meal may occur, which is the effect size found in a meta-analysis investigating the impact of kcal labelling on energy consumed during a meal with a range of available food options – i.e., the most similar design to the present study. The most up to date evidence of an effect of PACE labelling on energy consumed from foods/drinks is a meta-analysis of two studies and showed a significant reduction of 14.4%. Due to the small number of participants included in this meta-analysis, we conservatively powered our study to be able to detect an 8% reduction for both type of labels (kcal, PACE or kcal and PACE).

We will run a two-level mixed model including 18 trials (level 1) per participant (level 2) and compare self-served energy in each of the four trial arms (control, kcal labelling, PACE labelling, kcal and PACE labelling). We estimate SD of 300 kcal for self-served energy at level 1 and level 2 based on average SD of energy consumed during experimental meals [11]. A sample size of 1,600 participants with $\alpha = 0.05$ will allow to detect a 8% energy reduction between any of the four groups at power = 0.80. It will also allow to detect a small effect ($f=0.07$) of the interaction between the interventions and higher educational qualification education at power = 0.80 (MLPowSim) [39].

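### Label effects within each education group are obtained only after a significant interaction, although the first primary hypothesis predicts a reduction in both groups

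*Combined protocol and SAP*

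**What the plan says.** Section 2 gives separate primary hypotheses. The first is that labelling will "result in reduced total self-served energy among both participants of lower and higher SEP". The second concerns a difference between groups: "Kcal and PACE labelling will exert a stronger effect on self-served energy among participants of higher compared to lower SEP".

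Section 7.5 fits one mixed model with labelling (four levels), education (two levels) and their interaction. Two rules then decide what follows.

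- Separate models by education: "If the interaction is significant, analyses will be stratified by" highest qualification.
- Pairwise comparisons: "If there is a main effect of the labelling intervention in one of the above linear mixed models". They carry a Bonferroni correction that depends on how many comparisons are made ("e.g., 12 comparisons: $0.05/12=0.004").

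No other section asks for label effects within an education group. The sensitivity analyses (7.6) and the alternative SEP measures (7.7) vary or repeat the main analysis. The moderated mediation (7.7) also needs a significant interaction. Section 7.9 gives power for differences between whole arms and for the interaction, but not for a label effect within one education group.

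**The concern.** The first hypothesis is a statement about each group; the second is about the difference between them. Section 7.5 lets the test of the second decide whether the first is examined group by group. That fails in two ways.

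- **Equal effects.** If labels work equally well in both groups, the first hypothesis is true and the interaction is null. The gate then stays shut in about 95% of trials, so the direct evidence for the hypothesis is not produced.
- **Effect in one group only.** A non-significant interaction is compatible with a response confined to higher-SEP participants. The plan would then give either a diluted pooled effect or no follow-up, and in neither case show the reader how each group responded.

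Whether labelling helps lower-SEP participants as well is the question the trial was set up to answer. It should not depend on whether one p-value crosses 0.05.

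**Working it through.** **Inputs**

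- Alpha (section 7): "The level of significance will be set at $p < 0.05$ for the main and sensitivity analyses"; two-sided is assumed.
- SD (section 7.9): "We estimate SD of 300 kcal for self-served energy at level 1 and level 2", with 18 dishes per participant.
- 1,600 analysed, 400 per arm (section 7.9). Education is split 50/50 (section 4.1), so there are about 200 per label-by-education cell.
- Effect (section 7.9): the sample "will allow to detect a 8% energy reduction between any of the four groups at power = 0.80".

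**Participant-level SD.** All participants see all dishes, so dish effects cancel between arms. The SD of a participant's mean is √(300² + 300²/18) = 308.2 kcal.

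**The plan's own figures**

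- Pooled contrast at 80% power: (1.960 + 0.842) × 308.2 × √(2/400) = 61 kcal. This is 8% only if the no-label mean is 61/0.08 ≈ 763 kcal. The documents give no such mean.
- Interaction at f = 0.07: λ = 1,600 × 0.07² = 7.84. Noncentral F power is 0.80 on 1 df and 0.64 on the 3 df of the planned 4 × 2 test. The stated 0.80 therefore matches a 1-df contrast.

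**Equal effects in both groups.** The interaction is null, so P(non-significant) = 1 − 0.05 = 0.95.

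**Illustration: every label cuts 61 kcal in higher SEP and 0 in lower SEP (assumed)**

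- *Interaction.* The differences between groups across the four arms are (0, 61, 61, 61), whose population SD is 61 × √0.1875 = 26.4. So f = 26.4/(2 × 308.2) = 0.043 and λ = 1,600 × 0.043² ≈ 2.94. Power on 3 and 1,592 df is 0.27, so the test is non-significant in 73% of trials.
- *Pooled label effect.* The arm means differ by 61/2 ≈ 30 kcal, so f = 30.5 × √0.1875/308.2 = 0.043. The noncentrality is the same and power is again 0.27.
- *Both gates.* In a balanced design the two tests are practically independent:

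| Interaction | Pooled label effect | What 7.5 produces | Share |
|---|---|---|---|
| Significant | either | models by education | 0.27 |
| Not significant | significant | pooled follow-up, about 30 kcal | 0.73 × 0.27 ≈ 0.20 |
| Not significant | not significant | no follow-up | 0.73 × 0.73 ≈ 0.53 |

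A simulation of both tests gave the same shares (0.20 and 0.53).

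**If 300 kcal is the total SD, split equally (212 per level).** The participant-mean SD is √(212² + 212²/18) ≈ 218 and λ ≈ 5.89. Interaction power is 0.51, so 49% are non-significant: about 25% with a pooled follow-up and about 24% with none.

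**How large must the difference be?** With 300 kcal at both levels and all three labels differing equally by education, the interaction is more likely non-significant than significant until the groups differ by about 86 kcal. At f = 0.07 the difference is 0.07 × 2 × 308.2/√0.1875 ≈ 100 kcal.

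**Precision within one group.** SE = 308.2 × √(2/200) = 30.8 kcal, so the 95% interval is ±1.96 × 30.8 ≈ ±60 kcal. Power for 61 kcal is Φ(61.06/30.8 − 1.96) = 0.51 at 0.05 and Φ(61.06/30.8 − 2.865) = 0.19 at 0.05/12.

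**The case against.** **The group effects are already in the model.** The main model contains the interaction, so group-specific effects can be computed from it. The first hypothesis is also tested in pooled form, and the interaction is tested in every case. This stands: the gap lies in what the plan undertakes to report, not in what can be estimated. But a plan that never asks for the contrasts leaves them to choice after the results are known.

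**Following up simple effects only after a significant interaction is a common convention.** It guards against reading a significant result in one group beside a non-significant one in the other as a difference. That risk is real and shapes the fix. The convention nevertheless suits the second hypothesis; it does not answer the first.

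**A reader might infer that the gate stays shut in the most likely outcome.** The documents do not support that. They give no expected interaction size, the second hypothesis predicts an interaction, and at the plan's f = 0.07 significance is the likelier result (0.64 on 3 df, 0.80 on 1 df).

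**A reader might infer that all 73% of trials in the illustration would report a pooled 30 kcal as true of both groups.** They would not. The second gate, on the labelling main effect, has the same power in this scenario, so the pooled follow-up arises in about 20%. Nor does the plan say that a pooled effect will be read as holding in each group; it simply does not rule that out.

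**Judging the first hypothesis on significance within groups would often fail when it is true.** This stands. If labels cut 61 kcal in both groups, the chance of showing a given label's effect in both is 0.51² ≈ 0.26 at 0.05 and 0.19² ≈ 0.04 at 0.05/12.

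**Conclusion.** The concern holds as a gap between hypothesis and analysis. Followed as written, section 7.5 can leave a hypothesis about each education group with only a pooled answer, or with no follow-up. That happens in about 95% of trials when the effects are equal, a figure that needs no assumption beyond alpha = 0.05.

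The figures for an effect confined to higher SEP (73% non-significant; 20% with a diluted pooled follow-up and 53% with none) are an illustration. They rest on the 300/300 SDs, 200 per cell, and an assumed 61 versus 0 kcal. With 212/212 the figures are 49%, 25% and 24%. They do not establish how often the problem would occur in this trial, because the size of any interaction is unknown.

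It would also be too strong to say that the hypothesis is wholly untested, or that removing the gate makes it well tested: within-group precision stays limited at this sample size.

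**What to change.** In section 7.5:

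1. State that label versus no-label contrasts within each education group will be estimated from the main model and reported with confidence intervals, whatever the interaction p-value.
2. State that the interaction test addresses only the second hypothesis, and that a pooled effect with a non-significant interaction will not be read as showing a reduction in each group.
3. Fix the multiplicity denominator for this family in advance, rather than letting it follow the number of comparisons made.
4. State the expected precision (SE about 31 kcal, 95% interval about ±60 kcal under the plan's SDs). Present the contrasts as estimates, and say that non-significance in one group will not be read as no effect or as a difference between groups.

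The cost is SAP wording and a few LSMEANS or ESTIMATE statements in the planned PROC MIXED model, with no new data. The price lies in interpretation: if the sponsor wants these contrasts to be decisive tests, the sample is too small. On the same SDs, 80% power for 61 kcal in one group needs 401 per arm per education group at 0.05 and 701 at 0.05/12, against about 200 planned.

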6. STUDY FLOW

RECRUITMENT (Prolific)	
 ▪ Predefined screening questions of Prolific website will be used to target the sample (Appendix B) ▪ Participants who meet the inclusion/exclusion criteria will be emailed by Prolific and/or offered to complete our study on their Prolific account (Appendix C) ▪ Eligible participants who want to take part on the study will click on the start button and be redirected to our study website (Inquisit)
INFORMED CONSENT	
 ▪ Participants will read the information sheet (Appendix D) ▪ Participants who want to proceed will tick a consent box (Appendix E)
RANDOMISATION	
 ▪ Participants will be equally randomised and allocated to one of the four experimental groups using Inquisit software
BASELINE ASSESSMENTS	
 ▪ Participants will complete a baseline questionnaire on demographics (Appendix G)
MEAL CHOICE TASK	
 ▪ Instructions will be displayed (Appendix H) ▪ Meals will be displayed in randomised order

	Energy labelling (kcal+/PACE-)	PACE labelling (kcal-/PACE+)	Energy and PACE labelling (kcal+/PACE+)	No labelling (kcal-/PACE-)
EXECUTIVE FUNCTION	Tasks randomised in order: 
 ▪ Inhibition (Stroop task) ▪ Working memory (backwards digit-span task) 			
HEALTH MOTIVATION	
 ▪ Health and weight control subscales from the Food Choice Questionnaire (Appendix I) 			
PHYSICAL ACTIVITY LEVEL	
 ▪ International Physical Activity Questionnaire – Short Version (IPAQ-SF) (Appendix J) 			
FAMILIARITY AND LIKING	
 ▪ For each dish: 
 ○ Familiarity (Appendix K) ○ Liking rating (Appendix L) 			
DEBRIEFING QUESTIONNAIRE	
 ▪ Aim guessing in an open-ended response format (Appendix M) ▪ Questionnaire (Appendix M) 			
ADDITIONAL MEASURES	
 ▪ Interoception preliminary survey¹ (Appendix N) 			
DEBRIEFING TEXT	
 ▪ Tell the participants what the study was about (Appendix O) 			
DATA MANAGEMENT	
 ▪ The result files will contain: 
 ○ Participant unique ID ○ Experimental condition participant is directed to ○ Amount of self-served food ○ Answers to questionnaires 			

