In a previous study we conducted at virtual fast food restaurants [40], we found small-to-medium correlation between level of education and healthiness motivation ($r=0.17$) and small-to-medium correlation between healthiness motivation and kcal ordered ($r=-0.25$). Because evidence of a relationship between SEP and physical activity is mixed [41], we hypothesize small-to-medium correlation. Empirical estimates of sample sizes needed for 0.8 power in mediation analyses indicate that samples of ≈ 380 are sufficient to detect mediation through pathways that are small and small-to-medium in statistical size using bias-corrected bootstrap tests [42]. Thus, a sample of 1,600 participants (i.e., 400 per experimental condition) would allow for adequate power in our planned moderated mediation analysis.

We will recruit a sample of 1,800 participants (who consent to take part in the study) to account for potential data loss due to dropouts and failed quality controls (approx. 10%) resulting in a minimum sample of 1,600 participants for analyses. However, if we experience a greater loss of data than

expected, we will continue to recruit participants until we achieve the required sample size of 1,600 participants.

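### After the overall label-by-education test, no planned comparison shows which label's effect differs by SEP, or in which direction

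*Combined protocol and SAP*

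**What the plan says.** The second primary hypothesis, in section 2, is directional and names two labels: "Kcal and PACE labelling will exert a stronger effect on self-served energy among participants of higher compared to lower SEP".

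Section 7.5 addresses it through a mixed model with label (four levels), education (two levels) and "the interaction between labelling intervention and highest educational qualification". With these levels the interaction is a single test on 3 degrees of freedom. Section 7 sets the threshold: "The level of significance will be set at $p < 0.05$ for the main and sensitivity analyses".

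The next step is conditional: "If the interaction is significant, analyses will be stratified by" education, and "two linear mixed models will be fitted to examine the effect of the labelling intervention on self-served energy". Where a model shows a label main effect, six pairwise comparisons follow: three of a label against no label, two of the combined label against a single label, and kcal against PACE. The Bonferroni example, "e.g., 12 comparisons: $0.05/12=0.004", fits six pairs in each of two education groups.

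No other section fills the gap:

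- Section 7.6 varies the main model, and 7.7 first repeats it with income and subjective status.
- The moderated mediation contrasts in 7.7 concern indirect effects through a mediator, and run only after a significant interaction.
- The ANOVAs in 7.8 concern self-reported influence, not self-served energy.

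**The concern.** The interaction test asks whether the pattern of label effects differs between education groups in any way. It can be significant because of one label alone, including the combined arm, and with the gap in either direction. To say that kcal or PACE labelling favours higher SEP, one must compare that label's effect between the groups, and none of the 12 follow-up tests does so.

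What is left for label-specific statements is the pattern of significance in two separate models. A label significant in one group and not in the other is weak evidence that its effect differs, because each within-group test has limited power and the two can disagree by chance. At stake is the study's equity question: which label, if any, widens the gap, in which direction and by how much.

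**Working it through.** **Inputs from the documents.** SD 300 kcal at both levels and 18 dishes per participant (7.9). Analysed sample 1,600, with 400 per arm (7.9) and equal randomisation (section 6). Education split 50/50 (4.1), so about 200 per arm-by-education cell. Assumed: two-sided tests, equal cells, and a control mean of 600 to 763 kcal, which the documents do not give.

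**The plan's own figures.**

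- SD of a participant's mean = √(300² + 300²/18) = √95,000 = 308.2 kcal.
- Two arms of 400: SE = √(2 × 95,000/400) = 21.8 kcal. The difference detectable with 80% power at 0.05 is 61.1 kcal. This equals 8% if the control mean is 61.1/0.08 = 763 kcal, which is the source of the upper assumed value.
- Interaction at f = 0.07: noncentrality = 1,600 × 0.07² = 7.84. Power is 0.799 with 1 numerator df, matching the stated 0.80, and 0.643 with the 3 df of the planned test. On this definition the 3-df test needs f = 0.083, or about 2,230 participants at f = 0.07. The plan's power came from simulation and its definition of f is not shown, so this is a point to clarify, not a demonstrated error.

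**What the stratified follow-up does with a label that has no gap.**

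- Within one education group, label against none: SE = √(2 × 95,000/200) = 30.8 kcal.
- At 763 kcal an 8% cut is 61.0 kcal. The critical value at 0.05/12 is 2.865, so power = Φ(61.0/30.8 − 2.865) = 0.19. At 600 kcal (48 kcal) it is 0.095.
- If the two groups' tests are treated as independent, the chance that exactly one is significant is 2 × 0.19 × 0.81 = 0.31, or 2 × 0.095 × 0.905 = 0.17.

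A simulation (normal approximation, 400,000 trials per scenario) added the interaction gate, the label main-effect test in each group, and a threshold of 0.05/6 or 0.05/12 according to how many comparisons are made. Truth: kcal and combined cut 8% in both groups; PACE cuts 0% in lower and 16% in higher.

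| Control mean | Interaction significant | Kcal significant in exactly one group* | Direct kcal contrast at 0.05/3 falsely significant* |
|---|---|---|---|
| 763 kcal | 83% | 34% | 2.0% |
| 600 kcal | 61% | 23% | 2.7% |

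*Among trials with a significant interaction.

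About half of the one-group-only results run in the hypothesised direction (18 of 34 points at 763 kcal). If kcal and combined cut 12% in both groups instead, the one-group-only figures are 52% and 48%.

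**What the direct contrast can and cannot do.**

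- (Label minus none, higher) minus (label minus none, lower): SE = √(4 × 95,000/200) = 43.6 kcal.
- Detectable at 80% power and 0.05/3: 141 kcal, that is 141/763 = 18.5% or 141/600 = 23.5% of the control mean.
- Power for an 8-point gap at 0.05/3 (critical value 2.394): Φ(61.0/43.6 − 2.394) = 0.16 at 763 kcal; Φ(48/43.6 − 2.394) = 0.10 at 600 kcal.

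**One averaged any-label contrast against the 3-df test, at 763 kcal.** If all labels share an 8% v 16% gap, power is 40% v 27%. If only PACE differs (0% v 16%), it is 21% v 83%.

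**The case against.** The strongest reply is that the plan does not merely compare p-values between subgroups. A formal interaction test comes first, and stratification follows only if it is significant. If no label has an SEP gap, the stratified output can mislead in at most about 5% of trials. That stands: the gap lies in locating and signing the difference after a valid gate.

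Other points also stand, at least in part:

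- A reader might infer that the plan would attribute a gap to labels that have none. The documents do not support that. Section 7.5 lists tests and states no rule for reading discordant groups; it leaves the reading open.
- A reader might infer that the gap is never estimated. The main model already contains the three label-by-education coefficients. What is missing is their pre-specified reporting, with a multiplicity rule.
- The hypothesis can be read jointly for labelling of either kind, in which case the interaction with description is weak but not absent. The per-label reading is natural, since the sentence names both labels.
- The size depends on the scenario. With PACE at 8% v 16% and other labels at 8% in both groups, the interaction is significant in only 27% of trials at 763 kcal. Kcal is then discordant in 12% of all trials, about 6% in the hypothesised direction.
- The direct contrasts have little power for a gap of the planned size.

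None of this supplies the missing between-group comparison.

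**Conclusion.** The concern holds in a limited form. The interaction is a sound overall test of whether label effects differ by education. The follow-up cannot say which label differs, because it never compares a label's effect between the groups. This rests on the text alone. The rates rest on the plan's SDs, equal cells of 200, the assumed control mean and the chosen truths. Under those, an equal kcal effect looks group-specific in 23–34% of trials that pass the gate, against 2–3% for a direct contrast. The design, data, model and gate remain usable, and the low power of the direct contrasts limits what any follow-up can show. Severity: should-fix.

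**What to change.** Amend section 7.5 as follows:

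1. Keep the 3-df interaction as the overall test.
2. From the same full model, pre-specify three 1-df contrasts, for kcal, PACE and combined: (label minus no label in higher education) minus (label minus no label in lower education). Report each estimate with a confidence interval and a p-value adjusted for three contrasts.
3. Base label-specific statements about the second hypothesis on these contrasts, and keep the stratified results as description.
4. State that each contrast has an SE of about 43.6 kcal and about 10–16% power at 0.05/3 for an 8-point gap. The intervals should therefore carry the interpretation, and a non-significant contrast must not be read as no gap.
5. If wanted, report the averaged any-label contrast as a supplement. It should not replace the interaction test, because it gains power only when the labels share the gap.
6. In section 7.9, say whether the 0.80 power at f = 0.07 refers to a 1-df contrast or to the 3-df test.

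The cost is SAP wording and three ESTIMATE statements in the PROC MIXED model already planned. No new data are needed.

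### Holm's step-down could replace single-step Bonferroni for the pairwise label contrasts: same familywise control, a modest and scenario-dependent power gain, one sentence to change

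*Combined protocol and SAP*

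**What the plan says.** Section 7.5 fits a mixed model with labelling (four levels), education (two levels) and their interaction. If the interaction is significant, separate models are fitted for lower and higher education. The pairwise tests are gated: "If there is a main effect of the labelling intervention in one of the above linear mixed models we will follow up this main effect". Six contrasts are then listed: each label against none, the combined label against each single label, and kcal against PACE. For these, "We will apply a Bonferroni correction to the level of significance based on the number of pairwise comparisons made". The worked example has 12 comparisons, giving 0.05/12, rounded to 0.004. No step-down or closed procedure is mentioned, and no simultaneous confidence intervals are specified.

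These contrasts carry the primary hypotheses in section 2, including "PACE labelling will exert a stronger effect on self-served energy than kcal labelling".

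Section 7.9 states that 1,600 participants at alpha 0.05 "will allow to detect a 8% energy reduction between any of the four groups at power = 0.80". It does not use the Bonferroni level, and it gives neither a control mean in kcal nor an expected effect for the combined label.

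**The concern.** Single-step Bonferroni holds every contrast to 0.05 divided by the full count, even after some null hypotheses have been rejected. Holm orders the p-values and compares them in turn with 0.05/6, 0.05/5, 0.05/4 and so on, stopping at the first failure. The first threshold equals Bonferroni's and the later ones are larger. So whatever Bonferroni rejects, Holm rejects too, and the familywise error stays at or below 0.05 for any configuration of true nulls and any dependence between the tests.

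At stake is some power on the contrasts that answer the primary hypotheses. The contrasts most likely to benefit are those of middling strength, such as kcal v none and PACE v kcal when PACE v none is already clear.

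**Working it through.** **Inputs.**
- SDs, section 7.9: "We estimate SD of 300 kcal for self-served energy at level 1 and level 2"; 18 dishes per participant.
- Sample size, section 7.9: "a sample of 1,600 participants (i.e., 400 per experimental condition"). A 50/50 education split (section 4.1) gives about 200 per arm per stratum.
- Effects, section 7.9: 8% as the design target for every label; 8.4% (kcal) and 14.4% (PACE) as cited evidence.
- Assumed: two-sided tests, a control mean, and a combined-label effect.

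**1. The plan's own figures.** 0.05/12 = 0.00417, which agrees with the stated 0.004; 0.05/6 = 0.00833. The 0.80 power cannot be reproduced directly because no control mean is given, so I solve for the mean it implies:
- SD of a participant mean = √(300² + 300²/18) = 308.2 kcal.
- SE of a difference between two arms = 308.2 × √(2/400) = 21.8 kcal.
- Difference detectable with 80% power at 0.05 = (1.960 + 0.842) × 21.8 = 61.1 kcal.
- Implied control mean = 61.1/0.08, about 763 kcal.

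This mean is slightly too high for the task. Servings run from 20 to 1000 kcal (section 5.1), so at a mean of 763 the variance of one serving cannot exceed (1000 − 763) × (763 − 20) = 176,091. The plan's two SDs imply 300² + 300² = 180,000, which allows a mean of at most about 755. I therefore treat 763 as the upper end and also show 600 kcal.

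**2. Power for 8% at the levels actually used.**

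| Control mean | alpha 0.05, 400/arm | 0.05/6, 400/arm | 0.05/12, 200/arm |
|---|---|---|---|
| 763 kcal | 80% | 56% | 19% |
| 600 kcal | 60% | 33% | 9.5% |

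For example, at 763 kcal and 0.05/6: Φ(61.1/21.8 − 2.638) = Φ(0.16) = 56%.

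**3. Bonferroni against Holm, six-test family.** Simulation of at least 100,000 trials per scenario, with an omnibus gate at 0.05 and then either procedure:

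| Scenario | Contrast | 600 kcal: Bonferroni → Holm | 763 kcal: Bonferroni → Holm |
|---|---|---|---|
| 8% in every label arm | each label v none | 32.7 → 34.7% | 56.4 → 59.2% |
| 8.4% / 14.4% / combined 14.4% | kcal v none | 37.4 → 44.1% | 61.8 → 70.9% |
| same | PACE v kcal | 16.1 → 21.4% | 29.4 → 39.1% |
| same | PACE v none | 90.6 → 91.7% | 99.2 → 99.4% |

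The Bonferroni column can be checked by hand. For kcal v none at 763 kcal, the difference is 0.084 × 763 = 64.1 kcal and Φ(64.1/21.8 − 2.638) is about 62%. For PACE v kcal it is 0.060 × 763 = 45.8 kcal, giving about 30%.

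**4. Twelve-test family, about 200 per arm per stratum.**

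| Scenario (both strata) | Contrast | 600 kcal: Bonferroni → Holm | 763 kcal: Bonferroni → Holm |
|---|---|---|---|
| 8% in every label arm | each label v none | 9.5 → 9.9% | 18.9 → 19.9% |
| 8.4% / 14.4% / combined 14.4% | kcal v none | 10.9 → 12.7% | 21.6 → 25.8% |
| same | PACE v kcal | 4.5 → 5.4% | 8.4 → 10.8% |

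With effects halved in the lower stratum and multiplied by 1.5 in the higher one, the largest gain is 2.7 points at 600 kcal and 3.7 at 763. Across all the stratified scenarios, the largest gain within a scenario runs from 0.4 to 4.1 points.

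**5. Sensitivity to the combined label.** At 763 kcal with the cited single-label effects, the largest Holm gain is 8.4 points if the combined effect is 8.4%, 9.6 if it is 14.4%, and 21.0 if the two effects add (22.8%).

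**The case against.** The strongest reply is that nothing here is wrong. Bonferroni is valid, transparent and fixed in advance, and the worked example is correct. A reader might infer that the plan fails to control error or contains a mistake; the documents do not support that.

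A reader might also take a gain of about 10 points as the general figure. It is not. It needs the 14.4% PACE effect, which section 7.9 cites but declines to rely on because the evidence is small, together with an assumed combined effect and a control mean at the edge of what the scale allows. Under the plan's own 8% alternative the gain is 2 to 3 points, and kcal and PACE then do not differ, so there is no power to gain on that contrast. Nor is 10 a ceiling, as the additive case shows.

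The practical drawbacks stand. Holm has no simple matching simultaneous intervals, so a contrast can be significant while its Bonferroni-width interval includes zero. A contrast's status can also turn on another contrast's p-value, which makes the comparison of significance patterns in section 7.6 harder to read. Because the plan specifies no simultaneous intervals, the first cost is small here.

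Shaffer's refinement would gain more in the six-test family (63% against Holm's 59% with 8% everywhere at 763 kcal). However, its divisors depend on the logical structure of the family and, in the gated form, on a single omnibus test. Holm carries over to the 12-test family unchanged, and offering both would leave the choice to the analyst.

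**Conclusion.** This is a cheap improvement, not an error. That Holm rejects at least as much as Bonferroni at the same familywise 0.05 holds without any assumption about means or SDs, provided both use the same family of tests. The size of the gain is conditional: about 2 to 3 points per label v none under the design alternative, about 5 to 10 points on kcal v none and PACE v kcal under the cited effects with the combined label at 14.4%, and about 0.4 to 4 points in the stratified family. All of this assumes control means of 600 to 763 kcal and the plan's SDs.

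A reader might infer that the change repairs the power of the pairwise tests. It does not. At 763 kcal, moving from 0.05 to 0.05/6 costs 80 − 56 = 24 points for an 8% reduction, and Holm returns about 3 of them. The mismatch between the alpha in section 7.9 and the adjusted level in section 7.5 is the larger issue and needs its own answer.

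**What to change.** In section 7.5, replace the Bonferroni sentence with:

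> Pairwise p-values will be adjusted by the Holm step-down procedure within the set of 6 comparisons (12 if stratified) at familywise 0.05.

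Fix this before outcome data are seen, and name one procedure only. State the family count explicitly for the case where only one education stratum shows a labelling effect. The present text counts the comparisons made, which could then mean six, and Holm on 12 could reject less than Bonferroni on six.

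The cost is one sentence, with no new data, model or recruitment. If confidence intervals are reported for the contrasts, say how they are constructed and that they need not agree with the Holm decisions.
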